5.1.2. Injection Site Pain

For the purpose of this protocol, injection site pain will include pain associated with insertion of the needle, injecting of the drug, and any pain or tenderness at/around the injection site. On the day of injection (Day 0) injection site pain will be evaluated twice: immediately after (ie, as soon as possible but no later than 10 minutes upon removing the needle) and 1 hour (± 5 minutes) after

each injection (right before the next injection). Subjects will assess their injection site pain using an 11-point NRS by indicating a number between 0 (no pain) and 10 (worst pain). In addition, 1 hour after the fourth (final) injection subjects will provide an overall ranking of all four administrations from least [1] to most [4] painful. Thereafter, injection site pain will be evaluated by self-reports on Days 1, 3, 7, and 14, Month 3 and 6, and at additional visits, if appropriate. If the subject reports injection site pain at any of these visits, she will be asked to use the NRS to evaluate the intensity of pain in order to determine if it meets the definition of an adverse event.

5.2. Safety Assessments

The following safety and tolerability measures will be implemented throughout the study at the time points listed in Table 1.

- vital signs and weight will be measured at Day 0 and Month 6 and study exit
- adverse events and concomitant medications will be evaluated at Day 0, at Months 1 through 6, and at study exit
- information about adverse events and concomitant medications will not be actively solicited but documented if reported on Days 1, 3, 7, and 14 and unscheduled visits

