3.4.3. Follow-up/Final Visits

All subjects will return to the clinic on Day 1, Day 3, Day 7, Day 14, Month 1 and then monthly through Month 6. During Days 1, 3, 7, and 14 and Months 3 and 6 visits, ISRs and injection site pain for each of the four study injections will be evaluated following procedures outlined in Section 5.1. In addition, at monthly visits between Months 1 and 6, information on adverse event and concomitant medications will be collected. If the subject does not have any ISRs at Month 6, Month 6 will be her final visit, unless she agrees to return for additional follow up as detailed in Section 3.4.5. In addition to ISR, adverse event, and concomitant medication evaluation, her weight and vital signs will be measured at that time. Subjects who complete the study at Month 6 will be instructed to contact the clinic if any ISRs develop after their final visit. If any ISRs are identified or still ongoing at Month 6, monthly follow-up visits for ISR evaluation will be scheduled until the ISR is resolved or Month 18, whichever is earlier. In this case, the Month 6 procedures will be repeated at her final visit.

The following procedures will be performed during Follow-up/Final visits:

- injection sites evaluated for ongoing and/or new ISRs (Days 1, 3, 7, and 14 and Months 3 and 6 and at study exit)
- injection site pain assessed if self-reported (Days 1, 3, 7, and 14 and Months 3 and 6, and other visits if appropriate)

- adverse event and concomitant medication inquiry conducted (at Months 1, 2, 3, 4, 5 and 6 and at study exit)
- vital signs and weight measured (Month 6 and at study exit)

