4.5. Interim Data Reviews

The study will be overseen by an internal SRC, the composition and responsibilities of which will be detailed in a separate SRC Operational Plan. In addition to unplanned reviews that may be triggered by the occurrence of ISRs, serious and related adverse events, and/or injection site discoloration (hypopigmentation) events, the SRC may convene for a single planned review of interim data when approximately 50% of study subjects have been enrolled and treated. If, however, enrollment is predicted to take less than 2 months, then the interim review may instead be scheduled to occur after all subjects have been treated. At the time of any planned or unplanned interim review of data, the SRC may recommend that the trial be modified or halted to ensure the safety and well-being of study subjects. There will be no adjustment to type I error to account for any interim reviews of study data.

4.6. **Prior and Concomitant Therapy or Medication**

Any medication a subject uses between the enrollment and final visit will be recorded as a concomitant on the appropriate CRF. During scheduled Months 1, 2, 3, 4, 5 and 6 visits the investigator will ask subjects whether they have taken any medications, including over-the-counter medications, vitamins, or herbal or nutritional supplements, since the previous visit. During all other scheduled and unscheduled visits information on the use of concomitant medications will be documented only if reported by the subject. Generic or trade name, indication, route of IMP administration, dosage, and start and end dates will be recorded.

Subjects who are taking pain medications on a chronic basis will not be eligible for the study. There will be no prohibited medications during the study; however, application of bandages to injection sites will be discouraged.

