 - Injection site pruritus/itching if itching localized to the injection site requiring ≥48 hours treatment OR generalized itching causing inability to perform usual social and functional activities
 - Injection site erythema/redness of ≥ 5 cm in diameter (or ≥ 25 cm² surface area) or greater than minimal interference with usual social and functional activities
 - Injection site inducation/swelling of ≥ 5 cm in diameter (or ≥ 25 cm² surface area) or greater than minimal interference with usual social and functional activities
 - Any ISR that meets the definition of "serious adverse event"
 - Pre-existing diseases or conditions that worsen during the study.

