5.2.2. Recording and Reporting Adverse Events

For adverse event recording, the study period is defined for each subject as that time period from signature of the ICF through the end of the subject's follow-up period.

All adverse events that occur during the defined study period must be recorded on the source documentation and transcribed onto the CRF, regardless of the severity of the event or judged relationship to the IMP. For serious adverse events, the Serious and Protocol Defined Adverse Event Form must also be completed and the event must be reported immediately (See Section 5.2.5.3). The investigator does not need to actively monitor subjects for adverse events once their follow-up period has ended. Serious adverse events occurring in a subject after study discontinuation will be reported to the sponsor if the investigator becomes aware of them, following the procedures described in Section 5.2.5.3.

At the Day 0, Months 1 through 6 and study exit, the investigator must question the subject about adverse events by asking an open-ended question such as, "Have you had any unusual symptoms or medical problems since the last visit? If yes, please describe." At the scheduled Day 1, 3, 7, and 14 and unscheduled visits the information about adverse events will not be actively solicited but documented if spontaneously reported by the subject. All observed or reported signs and symptoms will be recorded individually, except when considered manifestations of a medical condition or disease state. A precise diagnosis will be recorded whenever possible. When such a diagnosis is made, all related signs, symptoms, and any test findings will be recorded collectively

as a single diagnosis on the CRF and, if it is a serious adverse event, on the Serious Adverse Event Form.

The clinical course of each adverse event will be monitored at suitable intervals until resolved or stabilized or returned to baseline, or until a determination of a cause unrelated to the treatment or study procedure is made.

The onset and end dates and times, action taken regarding IMP, treatment administered, and outcome for each adverse event must be recorded on the source documentation and transcribed onto the CRF.

The relationship of each adverse event to IMP and study procedures, and the severity and seriousness of each adverse event, as judged by the investigator, must be recorded as described below.

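### Between the end of the Day 0 visit and Day 14, adverse events away from the injection site and concomitant medications are recorded only if volunteered, and the Month 1 questions as worded do not look back that far

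*Protocol*

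**What the plan says.** Protocol Section 5.2 sets two modes of collection. At some visits inquiry is active: "adverse events and concomitant medications will be evaluated at Day 0, at Months 1 through 6, and at study exit". At the early visits it is passive: "information about adverse events and concomitant medications will not be actively solicited but documented if reported on Days 1, 3, 7, and 14". Section 5.2.2 repeats the passive rule for adverse events, and Section 4.6 repeats it for medications.

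At the active visits, Section 5.2.2 says: "At the Day 0, Months 1 through 6 and study exit, the investigator must question the subject about adverse events". This is done "by asking an open-ended question such as" the following: "Have you had any unusual symptoms or medical problems since the last visit". For medications, Section 4.6 has the investigator ask at Months 1 to 6 about anything taken, "including over-the-counter medications, vitamins, or herbal or nutritional supplements, since the previous visit". The medication wording is given as the procedure, not as an example.

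Section 3.4.3 fixes the order of visits: "All subjects will return to the clinic on Day 1, Day 3, Day 7, Day 14, Month 1 and then monthly through Month 6".

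**The concern.** Adverse event occurrence and concomitant medication use are secondary endpoints (Protocol Section 2.2.2.2), and the overall safety of same-day administration is a secondary objective (Section 2.1.2). The first two weeks follow four injections given on one day, carrying 120 + 60 + 104 = 284 mg of MPA in total (Section 1.3.2.8). If general events and medications in those weeks depend on the woman raising them, while Months 1 to 6 are actively asked, ascertainment differs by period and is weakest just after dosing. Tables of systemic events and medication use could then make the acute period look quieter than it was.

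One site-level definition is also touched. Section 5.2.1 counts as an adverse event "Injection site pruritus/itching if itching localized to the injection site requiring ≥48 hours treatment". That classification turns on treatment, and the protocol does not tell staff to ask about treatment at the visits where early itching would be seen.

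**Working it through.** The documents give no figure to reproduce here. The check is to map each visit to whether a general question is asked and how far back it reaches.

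| Visit | General adverse event question | Medication question | Period reached, as worded |
|---|---|---|---|
| Day 0 | Yes (5.2, 5.2.2); only if indicated (Table 1); not listed (footnote g) | Ongoing medication recorded (3.4.2); required (Table 1) | Up to that visit |
| Days 1, 3, 7, 14 | No; recorded if volunteered | No; recorded if volunteered | None |
| Month 1 | Yes | Yes | Day 14 to Month 1 |
| Months 2 to 6 | Yes | Yes | From the preceding visit |

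**The uncovered interval.** It runs from the end of the Day 0 visit to the Day 14 visit, about 14 days and four clinic visits. The documents do not state six months in days. Taking 182 days, 14 / 182 = 7.7% of core follow-up. Taking 180 or 183 days gives 7.8% or 7.7%. A woman who misses Day 14 would be asked about a longer span at Month 1, so the figure applies to attendance as scheduled.

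**How firm it is.** For medications the limit is firm, because Section 4.6 states the look-back as the procedure. For adverse events it is conditional. It arises if staff use the example wording and take the last visit to be Day 14, which is the natural reading but not a binding one.

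**What the plan promises for the same interval.** Protocol Section 5.2.1 says that any adverse event after consent will be recorded. Section 4.6 says the same of any medication used between enrolment and the final visit. SAP Section 6.4 treats an event as treatment emergent from the time of the first injection, and SAP Section 6.6 counts medications taken at any point in the study. The collection procedure does not fully support these definitions for the first two weeks.

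**What is still actively sought on Days 1, 3, 7 and 14.** Section 5.1.1 has blinded staff examine each site and ask non-leading questions about it at every study visit. Section 5.1.2 has site pain evaluated by self-report at the same visits, with NRS scoring if pain is reported. Redness, swelling, itching, bruising, discoloration and pain at the site are therefore outside the gap. What remains inside it is systemic or other non-site events, medication use, and the treatment duration that decides whether localized itching is an adverse event.

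**Day 0.** Sections 5.2 and 5.2.2 make it an active adverse event visit. Table 1 marks adverse event assessment on Day 0 and at each injection as if indicated, and footnote g lists inquiry only at Months 1 to 6 and study exit. These passages disagree.

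**The case against.** A reader might infer three stronger things, and the documents do not support them.

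- *That nobody asks about adverse events from Day 0 through Day 14.* Sections 5.2 and 5.2.2 require questioning on Day 0, and ongoing medication is documented at enrolment. The gap opens after that visit. The adverse event wording for Month 1 is only an example, so it does not confine the question to the time after Day 14.
- *That short-lived injection-site events would be lost.* Section 1.2.2 reports nine such events in the earlier study, lasting 4 to 5 days on average. Events of that kind are looked for at Days 1, 3, 7 and 14, so their duration says nothing about what the gap misses.
- *That the treatment comparison is biased.* Under SAP Sections 6.1 and 6.4, only events that can be ascribed to a particular injection are summarized or compared by treatment. Systemic events and medications cannot be so ascribed, because every woman receives all four products on one day.

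It can also be said that passive collection is stated consistently, that it is a deliberate choice in a small Phase 1 study with a site-reaction primary endpoint, and that volunteered events are recorded at four visits. Problems or treatment still present after Day 14 fall within the Month 1 inquiry. On itching, staff applying the definition to a reported itch may well ask about treatment, and the blinded clinician review in Section 8.6.1 checks adherence to definitions. The CRF and Study Manual, which might settle this, are not among the documents.

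All of this limits the concern. It does not remove it: no text requires anyone to ask about general events or medications in the two weeks after dosing, and the medication look-back is fixed short of them.

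**Conclusion.** The point holds as a risk of under-ascertainment, not an absence of data. For about 14 days (7.7% of six-month follow-up under the 182-day assumption), systemic adverse events and medication use rest on volunteered reports, and the Month 1 questions as worded do not recover them. This is firm for medications. For adverse events it depends on staff following the example wording.

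The percentage measures calendar time only. The documents give no rate of systemic events or medication use for this window, so the number missed cannot be computed, and one cannot say from them that this is the period of highest systemic event rate. The primary comparison of injection site reactions is largely unaffected. The one site-level exposure is the itching criterion of at least 48 hours of treatment, and there only if staff do not ask about treatment when itching is reported. The change is worth making because it costs little and makes two secondary safety endpoints more complete.

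**What to change.** Either of two wording changes closes the gap:

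1. In Protocol Sections 4.6 and 5.2.2, word the Month 1 adverse event and medication questions to run *since the day of your injections*. The cost is a slightly longer recall period at one visit.
2. Alternatively, ask the existing open-ended adverse event question and the medication question on Days 1, 3, 7 and 14, changing Sections 4.6, 5.2 and 5.2.2, Table 1 and footnote g to match. The cost is two short questions at visits that already take place, and probably a few more minor events and medications recorded. This option also brings treatment of itching into view when the site is examined.

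In either case, reconcile Table 1 and footnote g with Sections 5.2 and 5.2.2 on whether adverse events are actively asked about on Day 0. No analysis method or sample size changes. If the data have already been collected under the current wording, the clinical study report should say that non-site events and medications from after the Day 0 visit to Day 14 were captured without active inquiry.

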5.2.1. Definition of an Adverse Event

An adverse event is any untoward medical occurrence in a subject administered a pharmaceutical product, regardless of whether it has a causal relationship with the treatment.

In this study, any adverse event occurring after the subject has signed the ICF through the end of the follow up period will be recorded and reported as an adverse event.

An adverse event can, therefore, be any unfavorable and unintended physical sign, symptom, or laboratory parameter that develops or worsens in severity during the course of this study, or significant worsening of any concurrent disease, whether or not considered related to TV-46046, diluted TV-46046, TV-46046 Placebo or Depo-subQ 104. A new condition or the worsening of a pre-existing condition will be considered an adverse event. Stable chronic conditions (such as arthritis) that are present before study entry and do not worsen during this study will not be considered adverse events.

Accordingly, an adverse event can include any of the following:

- intercurrent illnesses
- physical injuries
- events possibly related to concomitant medication
- significant worsening (change in nature, severity, or frequency) of pre-existing conditions (Note: A condition recorded as pre-existing that is intermittently symptomatic [eg, headache] should be recorded as an adverse event if frequency of its occurrence increases during this study.)
- drug interactions
- laboratory or diagnostic test abnormalities, that result in the withdrawal of the subject from the study, are associated with clinical signs and symptoms or a serious adverse

event, or require medical treatment or further diagnostic work-up, or are considered by the investigator to be clinically significant (Note: Abnormal laboratory test results at the screening visit that preclude a subject from entering the study or receiving study treatment are not considered adverse events.)

- Any physical examination, vital signs measurement, or other safety assessment finding that is judged by the investigator as a clinically significant change (worsening) compared with a baseline value will be considered an adverse event. For the purpose of this study, the following will be considered adverse events:
 - Irregular vaginal bleeding that requires medical intervention or meets the definition of "serious adverse event" (See Section 5.2.5)
 - Injection site pain with a NRS score of 7 to 10
 - Injection site pruritus/itching if itching localized to the injection site requiring ≥48 hours treatment OR generalized itching causing inability to perform usual social and functional activities
 - Injection site erythema/redness of ≥ 5 cm in diameter (or ≥ 25 cm² surface area) or greater than minimal interference with usual social and functional activities
 - Injection site inducation/swelling of ≥ 5 cm in diameter (or ≥ 25 cm² surface area) or greater than minimal interference with usual social and functional activities
 - Any ISR that meets the definition of "serious adverse event"
 - Pre-existing diseases or conditions that worsen during the study.

5.2.2. Recording and Reporting Adverse Events

For adverse event recording, the study period is defined for each subject as that time period from signature of the ICF through the end of the subject's follow-up period.

All adverse events that occur during the defined study period must be recorded on the source documentation and transcribed onto the CRF, regardless of the severity of the event or judged relationship to the IMP. For serious adverse events, the Serious and Protocol Defined Adverse Event Form must also be completed and the event must be reported immediately (See Section 5.2.5.3). The investigator does not need to actively monitor subjects for adverse events once their follow-up period has ended. Serious adverse events occurring in a subject after study discontinuation will be reported to the sponsor if the investigator becomes aware of them, following the procedures described in Section 5.2.5.3.

At the Day 0, Months 1 through 6 and study exit, the investigator must question the subject about adverse events by asking an open-ended question such as, "Have you had any unusual symptoms or medical problems since the last visit? If yes, please describe." At the scheduled Day 1, 3, 7, and 14 and unscheduled visits the information about adverse events will not be actively solicited but documented if spontaneously reported by the subject. All observed or reported signs and symptoms will be recorded individually, except when considered manifestations of a medical condition or disease state. A precise diagnosis will be recorded whenever possible. When such a diagnosis is made, all related signs, symptoms, and any test findings will be recorded collectively

as a single diagnosis on the CRF and, if it is a serious adverse event, on the Serious Adverse Event Form.

The clinical course of each adverse event will be monitored at suitable intervals until resolved or stabilized or returned to baseline, or until a determination of a cause unrelated to the treatment or study procedure is made.

The onset and end dates and times, action taken regarding IMP, treatment administered, and outcome for each adverse event must be recorded on the source documentation and transcribed onto the CRF.

The relationship of each adverse event to IMP and study procedures, and the severity and seriousness of each adverse event, as judged by the investigator, must be recorded as described below.

5.2.3. Severity of an Adverse Event

The severity of adverse events including ISRs must be recorded as one of the following:

Mild: No	limitation of usual activities
----------	--------------------------------

Moderate: Some limitation of usual activities

Severe: Inability to carry out usual activities

5.2.4. Relationship of an Adverse Event to the IMP

The relationship of an adverse event to the IMP will be characterized per the table below where possible, noting it may not be possible to assess relatedness of systemic adverse events due to the cross-over nature of the study.

Term	Definition	Clarification
No reasonable possibility (not related)	This category applies to adverse events that, after careful consideration, are clearly due to extraneous causes (disease, environment, etc.) or to adverse events that, after careful medical consideration at the time they are evaluated, are judged to be unrelated to the IMP.	 The relationship of an adverse event may be considered "no reasonable possibility" if it is clearly due to extraneous causes or if at least 2 of the following apply: It does not follow a reasonable temporal sequence from the administration of the IMP. It could readily have been produced by the subject's clinical state, environmental, or toxic factors, or other modes of therapy administered to the subject. It does not follow a known pattern of response to the IMP. It does not reappear or worsen when the IMP is readministered.

Term	Definition	Clarification
Reasonable possibility (related)	This category applies to adverse events for which, after careful medical consideration at the time they are evaluated, a connection with the IMP administration cannot be ruled out with certainty.	 The relationship of an adverse event may be considered "reasonable possibility" if at least 2 of the following apply: It follows a reasonable temporal sequence from administration of the IMP. It cannot be reasonably explained by the known characteristics of the subject's clinical state, environmental or toxic factors or other modes of therapy administered to the subject. It disappears or decreases on cessation or reduction in dose. There are important exceptions when an adverse event does not disappear upon discontinuation of the IMP, yet an IMP relationship clearly exists. It follows a known pattern of response to the IMP.

